## **1.1.9 Persistence of symptoms in Post-COVID-19 Syndrome**

### **1.1.9.1 dyspnea**

The dyspnea symptom, popularly known as shortness of breath, can be characterized as a form of subjective experience of uncomfortable breathing, consisting of qualitatively distinct sensations that may vary in intensity, and may also present a range of symptoms not only with multiple interactions of physiological origin. , but also with multidimensional factors, such as psychological, social and environmental, often culminating in the situation described by some authors as “ total dyspnea ” (MARTINEZ *et al.*, 2004). However, expressions such as difficulty, effort, weight or discomfort to be able to breathe, sensation of shortness of breath, or hunger for air, feeling of oppression or tightness in the chest, are also widely used by patients in an attempt to describe the dyspnea symptom ( ZIEGLER, 2011) .

Some specific literature data show that dyspnea is usually present in up to 20% of the general population, being directly associated with increased morbidity and mortality, also generating limitations in physical and social activities and in the quality of life of individuals, especially when related to problems cardiac, pulmonary or even neuromuscular disorders, often within a hospital setting or even prolonged hospitalization (IOANNOU, LOCKE, *et al.* , 2020, NUNES, HERVÉ, *et al.* , 2020) .

In this context, it is common for individuals with cardiopulmonary complications to report dyspnea while performing physical activities, which can range from the mildest to the most strenuous, depending on the degree of punctual or systemic involvement involved (BOHN JÚNIOR, COSTA, *et al.* , 2020) . There are some plausible explanations found in the literature, based on the premise that during physical activities, there is greater consumption of oxygen and, consequently, greater production of CO2 (carbon dioxide) (BOHN JÚNIOR, COSTA, *et al.* , 2020, CORRÊA , KARLOH, *et al.* , 2011)

Other authors also suggest that, in response to the detection of high concentrations of CO2 and low concentrations of Oxygen, the bulbar respiratory center increases the respiratory rate as a way of compensating for homeostatic maintenance. In normal situations, this process does not generate discomfort, on the other hand, in the case of pathological contexts, where there is a deficit in cardiac or pulmonary functions, the respiratory rate and shortness of breath can be increased even in rest situations (DORNELES, 2018). ; SOUZA, VIEIRA et al., 2020) .

Not infrequently, there may be situations in which dyspnea can cause so much discomfort that individuals feel incapable of breathing with adequate depth and speed due to exacerbated ventilatory demand, and it is quite common for them to frequently report the perception that chest expansion when breathing in this difficult and reduced, as well as expiration (which should be a practically passive process) demands greater efforts than normal (SIMSIC, 2016) .

As an inevitable consequence, the increase in Respiratory Frequency (RR), together with shortness of breath, considerably affect the performance of physical and daily activities of individuals, generating a significant functional impact and directly implying in the reduction of the quality of life of the individuals involved (BOHN JÚNIOR, COSTA, *et al.* , 2020, ZIEGLER, 2011) .

### **1.1.9.2 Dyspnea assessment**

As already mentioned, dyspnea can be defined as a subjective perception of increased work of breathing, which generates a distressing sensation of shortness of breath, perceived as inadequate ventilation. Therefore, dyspnea, triggered when performing activities of effort, seems to be one of the most frequent complaints and tends to be more frequent among individuals who have impaired lung function, especially in the post-covid-19 period ( O'DONNELL *et al.* . *al.* , 2007).

The sensation of dyspnea in certain individuals during exertion leads to a progressive reduction in physical activity, and this condition can generate a vicious cycle, affecting not only the functional state and physical conditioning, but also the performance of their activities of daily living, having an impact. directly on the patient's quality of life (TROOSTERS *et al.*, 2005).

In this context, the literature provides a significant amount of instruments and scales to assess the degree of dyspnea in these individuals, whether through

subjective assessment, limitation of activities of daily living or functional disability (CABRAL, LOPES, *et al.* , 2017, PISSULIN, PACAGNELLI, *et al.* , 2018) .

Therefore, we can consider that among the unidimensional scales, the multidimensional instruments, the most used in practice are: the visual analogue scale (VAS), the Borg scale, the modified scale of the British Medical Research Council (MRC), basal index of dyspnea (BDI), transitional dyspnea index (BTI), in addition to the *PFSDQ* ( pulmonary functional status and dyspnea questionnaire) ( VELLOSO, COSTA, OZEKI, 2002)

**The Visual Analog Scale (EVA)**, created by Scott Co. Laboratory , in 1920, has been used to measure different subjective aspects such as mood, pain, anxiety and dyspnea , and since then it has been widely used in clinical practice to measure dyspnea both at rest and during exercise (AITKENS, 1969).

We have the modified Borg scale , which is characterized by being a subjective scale, adapted by BURDON, in 1982, to measure dyspnea both during exercise or in physical activities, since the measurement is made directly at the moment of that the patient is experiencing the sensation (BORG, 1998). The Borg scale seeks to assess the subjective sensation of exertion (also described as a sensation of respiratory fatigue), and covers a score from 0 to 10, where: 0 means no respiratory difficulty, while 10 represents maximum respiratory difficulty.

Because it is an extremely subjective scale, over time, and in order to allow a better understanding of the perceived exertion by the evaluated individual, the insertion of quantitative expressions of intensity was established so that there was a direct correlation between the numerical categories. and verbal descriptors (HIGBEE, DODD, 2020, SILVA, DIAS, *et al.* , 2011) . It is worth mentioning that the Borg scale includes instructions for its use, together with the structure to be evaluated, seeking not only to facilitate the individual's understanding, but above all to increase the accuracy of the response in relation to the subjective perception of effort during the proposed activities (CABRAL , LOPES, *et al.* , 2017, GOMES, SHUJMAN, *et al.* , 2019, LIMA DE, MAGALHÃES, *et al.* , 2019) .

The assessment of dyspnea in relation to limitations in performing routine activities requires some intersection between uni and multidimensionality, so that it is possible to quantify it. In this context, the most cited scale in the literature is the Modified Scale of the British Medical Research Council ( *MMRC - Modified Medical Research Council* ), created by English pulmonologists in 1960, and since then it has

been used to measure breathing difficulty in ADLs (activities of daily living) and perceived respiratory incapacity (BESTALL *et al.* , 1999, DA CAPITAL *et al.* , 2018).

MMRC scale is composed of only five items, with the patient choosing the item that corresponds to how much dyspnea limits their ADL, indicating their subjective degree of dyspnea by choosing a value between 1 and 5: 1 (only suffers from lack of breath during strenuous exercise), 2 (suffers from shortness of breath when walking quickly or walking up a gentle slope), 3 (walks slower than people of the same age because of shortness of breath or has to stop for breath even when walking slowly ), 4 (breathing pause after walking less than 100 m or after a few minutes) and 5 (feeling so short of breath that you no longer leave the house, or feel short of breath when getting dressed) ( KOVELIS, DEMETRIA *et al.* , 2008).

In practice, the MMRC scale is an instrument of easy applicability, understanding by the patient and reproducibility by the examiner, and consists of the correlated and adjective description of dyspnea during daily activities, which often fit the reality of individuals with breathing difficulties in basic activities. , how to leave the house, or even when dressing (CAMARGO, PEREIRA, 2010, KOVELIS, SEGRETTI, *et al.* , 2008, ZIEGLER, 2011; PISSULIN, PACAGNELLI, *et al.* , 2018) .

Regarding the multidimensional instruments for dyspnea assessment, we have the Basal Dyspnea Index (BDI) ( developed by MAHLER *et al.* , 1984) has been used to assess and measure the direct and indirect impact caused by dyspnea on individuals' lives, being divided into three distinct domains, however, correlating the magnitudes: functional disability, tasks and effort, facilitating a more detailed and multidimensional assessment of the impact of dyspnea on each individual's life. The BDI also has some specific characteristics, as it correlates a grade from 0 to 4 for each aforementioned domain, in addition to a field that includes, in addition to the subjectivity of the symptom, it also allows the association of the dyspnea symptom with other physical, emotional or behavioral aspects.

Regarding the use of multidimensional questionnaires for direct and correlated assessment of dyspnea, in the international literature, the following stand out: The - *Pulmonary Questionnaire Functional Status and dyspnea Questionnaire - Modified version* (PFSDQ- M), in its translated, adapted and validated version for Portuguese. For clarification and specification purposes, we have that PFSDQ-M ( Modified version of *Pulmonary Functional Status and dyspnea Questionnaire* ) is composed of three domains: influence of dyspnea on ADL, influence of fatigue on ADL (5 general and 10

specific items for each domain) and change in ADL compared to the period prior to the disease (10 specific items). With regard to these domains, the patient is instructed to indicate how much dyspnea and fatigue interfere with the 10 specific ADL items, - choosing a value between 0 and 10 for each activity, with the respective meanings: 0 (no interference), 1-3 (mild), 4-6 (moderate), 7-9 (severe) and 10 (very severe). In the third domain, the patient reports the impact on the change in ADL compared to the period before the disease, choosing for each activity a value between 0 and 10: 0 (as active as always in relation to this activity), 1-3 (small change), 4-6 (moderate change), 7-9 (extreme change) and 10 (no longer do this activity) ( KOVELIS, DEMETRIA *et al*, 2008).

After this personal and non-transferable stratification by the patient, not only is a partial score calculated, ranging from 0 to 100 for each of the three domains ( dyspnea, fatigue and change in ADL), and a total score is formed by the sum of the partial scores of the three domains, totaling a value that varies from 0 to 300. It is worth mentioning that there are five general questions in the dyspnea and fatigue domains that are merely informative and qualitative, and their answers are not counted in the questionnaire score. For purposes of interpretation, higher values on the scale indicate greater limitation in ADL ( LAREAU, MEEK, ROOS, 1998).

### **1.1.9.3 Musculoskeletal Change in COVID-19**

Excessive production of pro-inflammatory cytokines in hypercatabolic conditions is associated with oxidative stress, which promotes the production of corrosive molecules that cause severe damage to myocytes (WELSCH C *et al*., 2020). The exact dynamics underlying muscle wasting in COVID-19 are still unclear. However, the researchers suggest that muscle loss in COVID-19 patients is a result of a wide range of interrelated factors (Figure 1).

Aging, as well as metabolic and inflammatory disorders (diabetes, obesity, cardiovascular disease, cancer, etc.), are associated with baseline states of protein-energy malnutrition and hyperinflammatory systemic diseases that contribute to peripheral muscle dysfunction (PMD). In the context of COVID-19, these individuals are usually also the majority of affected patients and thus have ample possibilities of peripheral muscle dysfunction. Undoubtedly, elderly people affected by SARS-CoV-2,

especially the severe forms, are likely to express dramatic injuries to their muscle structure, especially in the late stages of the disease (PITSCHIEDER, L *et al.*, 2020; JIN M *et al.* , 2020).

[figure not shown]
The exact musculoskeletal consequences for patients with COVID-19 have not yet been fully established. Although the respiratory tract appears to be the primary site of infection, compromised alveolar epithelium in some COVID -19 patients can lead to the development of viremia , and cells in other tissues may be susceptible to direct viral infection . *al.*, 2020; DISSER *et al.*, 2020) .

In addition to the potential direct viral infection, infection -induced proinflammatory cytokines and signaling molecules can lead to pathological changes in skeletal muscle tissue. C-reactive protein (CRP) is a biomarker commonly used to assess inflammatory processes in general, and current studies have shown that critically ill patients with COVID-19 have much higher CRP levels than healthy individuals. Several of the pro-inflammatory signaling molecules known to be elevated in COVID-19 patients can also affect musculoskeletal tissue (DISSER *et al.* , 2020) .

Patients who needed to be admitted to an intensive care unit (ICU) or stayed in the hospital for long periods tend to have more musculoskeletal complications that require rehabilitation. The period of hospitalization is directly related to longer periods of hypomobility and/or immobility, resulting in fatigue, muscle weakness and polyneuropathy . (BARKER-DAVIES *et al.* , 2020; FELIPPE FELIX MEDIANO *et al.* , 2020) .

Myalgias and generalized weakness have been reported in symptomatic patients with COVID-19. Although some data have suggested that the occurrence of muscle pain does not increase with the severity of COVID-19, in patients with computed tomography (CT) or radiographic imaging of the abnormal lungs, myalgias were an important predictor of overall disease severity ( DISSER, et al., 2020) .

Even after hospital discharge, some patients report difficulties in activities of daily living (ADL), such as walking and climbing stairs. This suggests that SARS infection leads to deficits in both muscle strength and endurance, probably due to the pro-inflammatory effects of the viral infection and the deconditioning that occurs during the period of convalescence. The reduction in the functional capacity and physical fitness of these patients corresponded to falls in several health-related quality of life indices (DISSER *et al.* , 2020; LAU *et al.* , 2005) .

**Figure 1:** Pathophysiological hypothesis for peripheral muscle dysfunction in COVID-19.

(Source: MOHAMED ALI A & HIROSHI K, 2020)

#### 1.1.9.4 Peripheral muscle assessment

As previously discussed, peripheral muscle dysfunction has a substantial contribution to peripheral muscle fatigue. The impact of this dysfunction on muscle performance is developed by abnormalities in muscle structure, bioenergetics and function. Some important clinical implications are related to changes in muscle structure (mass) and function (strength and endurance), such as reduced exercise capacity, quality of life, and survival in several pulmonary conditions, including COPD, which we could similarly to assume similar changes in the dysfunctions induced by COVID-19. The etiology of these abnormalities appears to be multifactorial, involving factors such as deconditioning, hypoxia and/or hypercapnia, oxidative stress, senescence, hormonal dysfunction, systemic inflammation, chronic or repetitive use of drugs (corticosteroids) and nutritional depletion.

The involvement of inflammatory mediators in PMD is suggested by the observation that systemic inflammatory markers are related to poor contractile muscle performance in several pulmonary conditions such as COPD, ASTHMA and interstitial lung diseases ( RONDELLI RR *et al.*, 2009) . For example, quadriceps strength was negatively associated with IL-8 levels during exacerbation of lung diseases (SPRUIT MA *et al.*, 2003) and with IL-6 and TNF- $\alpha$  levels in the elderly (YENDE S *et al.*, 2006). In very critically ill patients, high CRP levels were associated with reduced strength, endurance and quality of life. On the other hand, in another study, it was evidenced that the marked weakness of the quadriceps was significantly related to the average daily dose of steroids used by the patients during the acute exacerbation of pulmonary diseases. The deleterious effects of steroids on skeletal muscle function have been attributed to the inhibition of protein synthesis and increased protein degradation. Other evidence suggests the role of oxidative stress in muscle dysfunction in hyperinflammatory lung diseases . COVID-19 is known to cause an inflammatory, multisystemic storm implicated over time in several peripheral dysfunctions, including muscle dysfunction. All determinants of muscle dysfunction in pulmonary diseases are summarized in Table 1.

determinant trigger	Abnormalities	dysfunction
hyperinflammatory stress	↑↑ pro-inflammatory cytokines such as IL1, TNF-alpha, IL-8, IL-6	↓muscle performance
Use of corticosteroids	↓protein synthesis and ↑muscle catabolism	↓muscle performance during exercise, worsening dyspnea and fatigue
Acute and/or chronic hypoxemia	↑inflammatory mediators, ↓ATP and muscle glycogen	↓muscular strength and endurance , ↓muscle performance but activities of daily living.
oxidative stress	Oxidant and anti-oxidant imbalance	↓muscular endurance
Immobility and sedative and neuromuscular blocking agents	↓type I fibers and ↓oxidative enzymes ↑IIx fibers ( hypotrophied )	↓muscular endurance and muscular ↓performance during exercise

**Table 1:** Metabolic and bioenergetic determinants of peripheral muscle fatigue in lung disorders and their consequences. (Modified from: RONDELLI RR *et al.*, 2009)

Currently, there is a wide variety of models, tests and exercise protocols being used, aiming to obtain parameters indicative of muscle fatigue in patients with COPD ( Vøllestad NK *et al.*, 1997).

Functional assessment methods of peripheral muscle fatigue basically involve three basic components:

- I) the muscle activation strategy: voluntary effort or exogenous stimulation
- II) the condition of the exercise (isometric, isoinertial or isokinetic )
- III) the exercise pattern: time and intensity, which may involve a single prolonged contraction or a series of repeated contractions

Most of the methods used in this evaluation in patients with pulmonary or cardiac diseases preferentially focus on the muscles of the lower limbs. It should be noted, however, that the function of the upper limbs remains relatively preserved in these patients.

#### *maximum voluntary contraction*

[figure not shown]
The assessment of muscle strength and endurance can be obtained by maximal voluntary contraction (MVC). This assessment can be done by instructing the patient to generate as much voluntary force as possible without altering muscle length (symmetrical test) or by encouraging the patient to perform a full range of motion with the greatest possible load (1RM test). In this evaluation, equipment such as tensiometers or dynamometers can be used to quantify the generated isometric force (if there is no change in muscle length). In the case of the 1 RM test, the highest load imposed and that the patient can complete and repeat is considered. As these are volitional techniques, external complicating factors, such as the patient's functional ability and motivation, can generate submaximal contractions and thus underestimate the analysis. However, due to the ease of execution, verbal encouragement and technical experience, little variability has been described in our tests involving maximal voluntary contraction (MVC). In patients with chronic pulmonary dysfunction, the loss of the ability to generate or maintain MVC during knee extension exercise has been representative of muscle fatigue. (SWALLOW EB *et al.*, 2007). Studies have used series of submaximal voluntary contractions in the evaluation of resistance and peripheral muscle fatigue. Usually, relative values of approximately 20-60% of MVC (1RM test or isometrically sustained maximal voluntary contraction ) are required to be sustained until exhaustion, maintaining cadence and rhythm constant or close to it. Resistance is measured by the time the task is maintained. The test should be stopped

when there is a failure to maintain the intensity of the contraction (5% drop) or inability to complete the range of motion or visually there are signs of muscle fatigue, such as fasciculations , for example.

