### **2.3.6.3 Quadriceps Muscle Endurance Test**

The quadriceps muscular endurance test will be performed after 30 min of rest after the 1 RM test. We will use a load of 40% of the load obtained in the 1 RM test, rounding up to the next higher load in case of load fractions.

The muscular endurance test will be performed in the same extension chair, with hips, ankle at 90° and knee flexed to ensure an angular velocity of 1'20°/s using the dominant lower limb ( LLd ). Volunteers will be instructed to count 1 second for LL extension and 1 second to return to flexion (angular velocity of 120°/s). The outcome of this test will be the time to exhaustion characterized by failure or inability to complete the range of motion.

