## 2.4 Outcomes

### 2.4.1 primary outcome

As variables for the primary outcome of this research, it will be the functional performance, resulting from the combination of the PCFS Scale with the Dynamometry of Pressure Para, Test of Strength and of Endurance of the quadriceps muscle.

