## 2.5 Data analysis

### 2.5.1 Sample size (calculation or justification)

The sample size calculation was done with the “ pwr ” package (CHAMPELY S, 2018) (R package , version 1.2-2, <https://CRAN.R-project.org/package=pwr> ). For the calculation, we considered the mean of 41.3, the standard deviation of 5.05 and a minimal clinically important difference of 4.7 kg between the means of maximum load in the maximal voluntary contraction test (OLIVEIRA IO, 2016) and power based on *Cohen 's model* of 0.8 with a standard deviation of 5.05. Assuming  $\alpha = 0.05$ ,  $\beta = 0.8$ , standard deviation = 5.05 and an effect size proposed by Cohen of 0.93.

This effect size " *d* " is calculated by:

$$d = [(Reference\ average + Minimum\ detected\ change) - reference\ average] / deviation - standard$$

$$d = [( 41.3 + 4.7) - 41.3] / 5.05 \Rightarrow d = 0.93.$$

*pwr* package . in R we have:

```
n = pwr.t.test ( n=NULL, d=0.93, sig.level =0.05, power=0.8, type=" two.sample ", alternative="
two.sided ")
```

$$n = 19.15925$$

$$d = 0.93$$

$$sig.level = 0.05$$

$$power = 0.8$$

$$alternative = two.sided$$

In this way, we use on=established and rounded up to the first integer immediately higher ( $n=20$ ) + 20% to cover any losses. Thus, the minimum number of patients needed in each group will be 24 patients.

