### **2.5.5 Statistical analysis plan**

Data analysis will be performed using the SPSS 23.0 program ( Statistical Package for Social Sciences ). Descriptive analysis will be performed for all variables (mean and standard deviation). General Linear Model ( GLMs ) with mixed design will be performed to compare treatment effect size between groups. The pairwise comparison comparisons ) will be performed to verify the mean difference between the Pilates Group and the Control Group in all variables in each period independently.

Intention-to-treat analysis was used using the *Last method. observation Carried Forward* (LOCF) for lost participant data. A significance level of 0.05 and a confidence interval of 95% will be adopted

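### Quadriceps endurance is an uncapped time to exhaustion, yet it is compared by raw means with no baseline covariate; log-scale ANCOVA is a cheap safeguard whose gain depends on unreported skew

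*Combined protocol and SAP*

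**What the plan says.** The operative definition is in section 2.3.6.3: "The outcome of this test will be the time to exhaustion characterized by failure or inability to complete the range of motion". The load is individual: "We will use a load of 40% of the load obtained in the 1 RM test". No maximum duration is given there. The literature review (section 1.1.9.4, under maximum voluntary contraction) describes such tests in the same way, "Resistance is measured by the time the task is maintained", but it is background and not an instruction for this trial.

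Section 2.4.1 makes endurance one of four parts of the primary outcome: "it will be the functional performance, resulting from the combination of the PCFS Scale with" handgrip dynamometry and the quadriceps strength and endurance tests. It gives no rule for combining them. The hypotheses in section 1.5 also name endurance.

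The analysis is in section 2.5.5. On summaries: "Descriptive analysis will be performed for all variables (mean and standard deviation". A mixed-design general linear model "will be performed to compare treatment effect size between groups", and pairwise comparisons serve "to verify the mean difference between the Pilates Group and the Control Group in all variables in each period independently". The section names no transformation, residual check, alternative method or baseline covariate.

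**The concern.** A time to exhaustion cannot fall below zero and here has no stated ceiling. Such a variable may be right-skewed, and training may lengthen it roughly in proportion to the patient's own time. If both hold, spread rises with the mean, a few long tests weigh heavily on a raw mean, and a model with one common error variance is inefficient. Comparing arms in each period independently also leaves the baseline measurement out of the 12-week contrast. The group-by-time test uses baseline only as a simple change.

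What is at stake is precision, and a summary that describes the typical patient, for one component of the primary outcome. The sample size was set on maximum load in kg, so nothing in the plan secures the power for endurance.

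**Working it through.** **The plan's own figure.** Section 2.5.1 uses a difference of 4.7 kg and an SD of 5.05, so d = 4.7/5.05 = 0.93. The stated call, "d=0.93, sig.level =0.05, power=0.8", two-sided, reproduces: n = 19.16, rounded up to 20, and 20 × 1.2 = 24 per group. This concerns strength only. I borrow d = 0.93 as a yardstick because the documents give no effect size for endurance.

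**Inputs.** From the documents: 24 per arm, two-sided alpha 0.05, d = 0.93, two time points. Assumed: coefficient of variation (CV) 0.3 to 1.0, baseline-to-12-week correlation r = 0.6, and the shape of the distribution.

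**What baseline adjustment buys, whatever the scale.** With equal variances, and relative to the 12-week comparison alone, the variance of the arm difference is multiplied by 2(1 − r) = 0.80 for a change score and by 1 − r² = 0.64 for ANCOVA. In a two-period mixed model the group-by-time test is the change-score test. At 24 per arm the signal for the 12-week comparison is 0.93 × √(24/2) = 3.22. For change it is 3.22/√0.80 = 3.60, and for ANCOVA 3.22/√0.64 = 4.03. Subtracting 1.96 gives normal-approximation power of about 90%, 95% and 98%.

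**What skew costs.** Simulation, 20,000 trials per setting. For lognormal times the log-scale SD is s = √ln(1 + CV²), which is 0.294, 0.472, 0.631 and 0.833 for CV 0.3, 0.5, 0.7 and 1.0. The effect is a multiplier exp(0.93 s), which is 1.31, 1.55, 1.80 and 2.17. In the counter-case times are normal with an additive effect of 0.93 SD, floored at 5 on a mean of 60. Power (%) at 24 per arm:

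| Times | CV | Raw, 12 weeks | Raw, group-by-time | Raw ANCOVA | Log ANCOVA | Log change |
|---|---|---|---|---|---|---|
| Lognormal | 0.3 | 86.9 | 94.8 | 96.4 | 97.3 | 94.0 |
| Lognormal | 0.5 | 84.9 | 93.8 | 95.1 | 97.4 | 94.2 |
| Lognormal | 0.7 | 81.6 | 91.2 | 92.3 | 97.1 | 93.8 |
| Lognormal | 1.0 | 76.7 | 86.3 | 87.5 | 97.5 | 94.2 |
| Normal | 0.2 | 88.5 | 94.2 | 97.4 | 97.0 | 90.5 |
| Normal | 0.3 | 88.1 | 94.3 | 97.3 | 96.0 | 85.4 |
| Normal | 0.4 | 88.2 | 93.9 | 97.0 | 94.7 | 78.7 |

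The first two power columns are the planned tests. With mild skew most of the gain comes from using baseline as a covariate (94.8 to 96.4 at CV 0.3, then 97.3 with the log). With strong skew nearly all of it comes from the log (86.3 to 87.5, then 97.5).

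**Influence.** In the lognormal case the two most extreme of 24 patients supply 41%, 46%, 51% and 57% of one arm's sum of squares at CV 0.3, 0.5, 0.7 and 1.0, against 36% under normality.

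**Type I error.** Null runs gave about 4% to 5.5% on both scales.

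**Other sizes.** At 20 per arm (24 less the loss allowance) and normal times, log ANCOVA falls short of raw ANCOVA by about 1 to 4 points (94.1 to 93.3 at CV 0.2; 94.4 to 90.3 at CV 0.4). A separate run with a lower floor gave 94 to 89 at CV 0.4. At 30 per arm, the size in section 2.3, the pattern is the same: 12-week raw power at CV 1.0 is about 85%, against 99% for log ANCOVA.

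**The case against.** The strongest reply is that skew and a proportional effect are assumed. The documents report no mean, SD, range or shape for endurance time. The load is set at 40% of each patient's own maximum, and the text does not say whether it is re-set at 12 weeks, so the form of any effect is open. A lognormal simulation favours the log by construction, and with normal times the log loses. Analysed as log change, the group-by-time test falls from about 94% to between 91% and 79%. All of this stands, and it makes the size of the loss conditional. The large losses, however, belong to log change scores. Log ANCOVA stays level with or above both planned tests in every setting in the table.

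That last result rests on r = 0.6. In the same simulation with r = 0.3, normal times and CV 0.4, log ANCOVA gave 86.7% against 88.6% for the raw 12-week comparison, a deficit of about 2 points.

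It could also be said that section 2.5.2 already lists the endurance test among the control variables. That list contains the strength and endurance tests, symptom scales, functional scale and quality of life, which are the measured outcomes, and section 2.5.5 does not put them in the model as covariates.

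A reader might infer that a few long performers will dominate the trial's result, or that the planned test is invalid. The documents support neither. The first needs marked skew that nobody has shown, and the null runs speak against the second. Nor can an effect on the primary result be worked out, since the combination rule is not given. The unit of analysis (seconds or otherwise) is not stated either.

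**Conclusion.** The point holds as a conditional loss of efficiency with a cheap remedy. The plan gives an open-ended, positive duration the same raw-scale treatment as every other variable and leaves its baseline value out of the 12-week comparison. If times are lognormal with a proportional effect, then at 24 per arm, d = 0.93 and r = 0.6 the gap to log ANCOVA is about 2 to 11 points for the group-by-time test and 10 to 21 points for the 12-week comparison, across CV 0.3 to 1.0. If times are near normal with an additive effect, the log itself brings no gain and costs about 0 to 3 points against raw ANCOVA. Baseline adjustment still helps there, with raw ANCOVA at about 97% against 94% and 88% for the planned tests. It is an improvement worth making before the data are analysed, and it also removes a later temptation to choose a scale after seeing the results.

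**What to change.** In section 2.5.5, state that quadriceps endurance time at 12 weeks will be compared between arms by ANCOVA on the log scale, with log baseline endurance time as covariate. Report the effect as a ratio of geometric means with its 95% confidence interval. Describe the times by median and quartiles for each arm and time point. Give the raw-scale ANCOVA, with raw baseline as covariate, as a sensitivity analysis. Do not use log change scores.

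The cost is two or three sentences and two computed variables in SPSS, with no new data, since baseline is already measured. The effect is read as a ratio rather than a time difference. If times prove near normal with an additive effect, the log version gives up about 0 to 3 points of power against raw ANCOVA at 24 per arm (up to 4 to 5 at 20 per arm). At the assumed correlation of 0.6 it remains no worse than the tests now planned.
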